CGM Group: Patients will wear a real-time Dexcom G6 CGM, which provide BG readings every 5 minutes for up to 10 days. In addition, patients will undergo POC testing before meals and bedtime per hospital protocol. Insulin therapy will be titrated based on daily CGM printouts, which will include BG readings, glycemic excursions, hypoglycemia and severe hyperglycemia values throughout the day. Patients will wear a CGM in the current approved insertion site, the abdomen, and in the upper arm, both during hospitalization (up to 10 days).

Primary and Secondary Research Outcomes:

The primary aim is difference between POC testing (standard of care) and CGM in glycemic control (efficacy outcome) and hypoglycemic events (safety outcome) during hospitalization:

- 1) Glycemic control, as measured by time in range between 80-180 mg/dl (efficacy outcome)
- 2) Clinically significant hypoglycemia <54 mg/dl (safety outcome)

Secondary outcomes include differences between groups in any of the following measures:

1. Nocturnal hypoglycemia < 70 mg/dl and < 54 mg/dl (between 22:00 and 06:00)
2. Number of hypoglycemia events (< 70 and 54 mg/dl)
3. Duration or time in hypoglycemia (minutes) during the day and night
4. Frequency and duration of time in hyperglycemia > 250 mg/dl
5. Percentage of BG readings within target BG of 80 and 180 mg/dl
6. Glycemic variability calculated by Standard Deviation, and MAGE
7. Differences in BG by CGM devices placed in the abdomen and upper extremity
8. Number of sensor removal for procedures/imaging, sensors failures, sensors dislodgments

9. After discharge: time in range (TIR), frequency of and time in hypoglycemia (TIHypo), frequency of and time in hyperglycemia (TIHyper), glycemic variability (GV)

Inclusion Criteria:

1. Males and females \geq 18 years admitted to a general medicine or surgical services.
2. Diagnosis of: T1D or T2D receiving insulin therapy during hospital admission.
3. Subjects must have a randomization BG $<$ 400 mg/dL without laboratory evidence of diabetic ketoacidosis (bicarbonate $<$ 18 mEq/L, pH $<$ 7.30, or positive serum or urinary ketones).
4. Patients with expected hospital length-of-stay of 2 or more days

Exclusion Criteria:

1. Patients with acute illness admitted to the ICU or expected to require admission to the ICU.
2. Patients expected to require MRI procedures during hospitalization.

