CGM – alarms and hypoglycemia protocol. We will use a real-time Dexcom CGM device with a modified transmitter able to store and transmit glucose data to different devices including a notebook/IPAD or computer desk located at the nursing station. **The hypoglycemia alarm** will be set at 80 mg/dl to alert the nursing staff and providers that a patient is at risk of hypoglycemia. If this occurs, the nursing staff will meet patient in the room to assess clinical status and signs/symptoms of hypoglycemia and will perform a POC glucose testing to confirm glucose values. Nursing staff will be instructed to document POC at the time and provide 15 grams of carbohydrates to treat and prevent a serious hypoglycemic event.

Patients in the Standard of Care group will wear a blinded CGM and without alarms, but BG levels will be recorded (in a blinded fashion). If a POCT BG value is $<$ 80 mg/dl, 15 grams of carbohydrates will be given as a preventive measurement to avoid clinically significant hypoglycemia.

An additional CGM alarm will be set up if $BG > 250\text{mg/dL}$ for one (1) hour. The alarms will be set up only for the research team following the participants assigned to real-time intervention. The research physician will determine if treatment changes need to be done and notify the nursing staff of such changes that require immediate attention.

Treatment randomization. Patients will be randomized using a computer-generated randomization table. Treatment randomization/assignment will be coordinated by the statistician [name]. A research person (not actively involved in recruitment) at each institution will follow a computer-generated block randomization table based on glucose levels ($BG \leq 200$ or $BG > 200\text{ mg/dL}$) at randomization.

Recommended Basal Bolus Insulin Protocol.

Patients will be treated with a basal bolus insulin regimen as previously reported ^{12,13}.

During the first day of study enrollment POC BG values will be used to start insulin dosing in both groups.

T1D TREATMENT PROTOCOL

- Patients will be T1D will be treated with basal bolus insulin regimen, given 50% basal (glargine or detemir) and 50% of rapid acting insulin (lispro or aspart) before meals. This will be adjusted at physician's discretion based on the patient's home insulin regimen.

T2D TREATMENT PROTOCOL

Patients T2D Treated with Insulin Prior to Admission

- Discontinue oral antidiabetic drugs on admission.

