 - g. Percentage of BG readings within target BG of 80 and 180 mg/dl (time in range)
 - h. Glycemic variability calculated by Standard Deviation, and MAGE
2. Diabetes treatment:
 - a. Number of patients receiving insulin
 - b. Insulin dosage (unit/day)
 - c. Use of oral agents
3. Clinical Outcome:
 - a. Hospital readmissions
 - b. Emergency room visits

Study Sites:

The study will be conducted in three academic institutions: Grady Memorial Hospital ([name] and [name]), Midtown Emory Hospital ([name]), and at the University of Maryland and VA Maryland Health Care System (PI: [name]).

IV. Statistical Methods

The present study is one of two projects aimed to investigate the role of CGM (Dexcom G6 CGM) in the management of patients with diabetes in non-ICU setting receiving basal bolus insulin treatment. These prospective studies will explore the efficacy of CGM compared to standard POC glucose testing in assessing glucose control (efficacy) and hypoglycemic events (safety) as well as in guiding insulin therapy in patients with diabetes during admission and after hospital discharge. [name], PhD at the School of Public Health at Emory University will conduct statistical analyses.

The primary efficacy endpoint is glycemic control measured by mean daily BG concentration and time in range between patients managed by POC testing (standard of care) and CGM. To show non-inferiority between POC and CGM in terms of glycemic control, we set the equivalence margin of 18 mg/dl (1 mOsm/l), from a view that a difference <18 mg/dl is usually not considered as clinically significant (12, 14, 16). Based on the results

from Rabbit medicine and surgery trials, it is reasonable to assume the standard deviation of mean daily BG is bounded above by 45 mg/dl. Assuming the true BG difference between the treatment groups is zero, and using one-sided, two-sample t-tests, we require 78 subjects for each treatment group to achieve 80% power. Accounting for 10% attrition rate, we would need 90 patients per treatment group, which means 180 subjects in total, to achieve >80% power in Aim 1.

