We will report baseline characteristics by hospital service (medicine and surgery), diabetes type, and risk factors for hypoglycemia. The rates of incidence of hypoglycemia will be calculated based on the data obtained by CGM and POC. Comparisons will be made with the use of Wilcoxon tests (or Kruskal-Wallis tests) and Chi-square tests (or Fisher's exact test) as appropriate. Multivariate linear regression will be conducted to assess the difference in continuous secondary outcomes between the two groups while other relevant covariates. To be eligible for analysis at least 70% of CGM values need to be available per day, with at least 2 eligible days of data per subject in each study arm (inpatient and outpatient). Glucose patterns will be analyzed based on the Ambulatory Glucose Profile, recently endorsed by an international expert as a standardized approach for CGM interpretation⁴⁴. Hospital glucose values after the first day of insulin treatment will be included in the analysis to allow us to have a full 24-hrs glucose profile and to avoid analyzing day-1 CGM values which may have lower accuracy. For clinical accuracy, CGM and POC BG will be paired and will be plotted in the Clarke Error Grid^{46,47}. Paired CGM and POC BG falling in the Zone A will be defined as "accurate", and in Zone B as "acceptable", with remaining values considered "not acceptable" if falling in Zone C, D, or E.

A total of 180 insulin treated patients will be included in this prospective study. Based on previous studies by our unit, we anticipate that 80% of patients will complete the inpatient and ambulatory arms of the study^{13,48}.

V. Methods and Procedures Applied to Human Subjects:

Potential Risk to Human Subjects

Hypoglycemia. The risk of hypoglycemia in non-ICU patients treated with basal-bolus insulin is between 12%–35%^{14,19,37,49}. In this analysis, hypoglycemia is defined as a BG or IG < 70 mg/dL. Clinical significant hypoglycemia is defined as BG or IG < 56 mg/dL. Severe hypoglycemia is defined as BG or IG < 40 mg/dL.

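### Randomization is blocked on baseline glucose, but no planned analysis names that factor; adjusting the non-inferiority comparison for it would add some precision at no data cost

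*Combined protocol and SAP*

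**What the plan says.** The paragraph on treatment randomization in section III states: "A research person (not actively involved in recruitment) at each institution will follow a computer-generated block randomization table based on glucose levels". The cut is at a randomization BG of 200 mg/dL. Under Study Sites, "The study will be conducted in three academic institutions".

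Section IV sets an 18 mg/dl margin on mean daily BG and sizes the trial with an unadjusted test: "using one-sided, two-sample t-tests, we require 78 subjects for each treatment group to achieve 80% power". The variability input is an upper bound: "it is reasonable to assume the standard deviation of mean daily BG is bounded above by 45 mg/dl". The significance level is not written down.

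The analysis paragraph names Wilcoxon or Kruskal-Wallis tests and chi-square or Fisher tests, without linking any of them to the margin. It then adds: "Multivariate linear regression will be conducted to assess the difference in continuous secondary outcomes between the two groups while other relevant covariates". That sentence lacks a verb before its covariates, does not list them, and covers secondary outcomes only. Neither the BG stratum nor continuous randomization BG appears anywhere in section IV.

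**The concern.** When allocation is balanced within strata of a prognostic factor, the two arms resemble each other more than simple randomization would make them. An unadjusted t-test does not credit that balance. It still charges the between-stratum variance to the standard error, so the non-inferiority test runs below its nominal error rate and gives up some power. Randomization BG is a natural prognostic factor for inpatient mean BG, and it must be known for every patient before the block table can be used.

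Pre-specification is also at stake. With the covariates unnamed, any adjusted version of the primary comparison would have to be chosen later, possibly with results in view.

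Finally, the text does not say whether each institution follows its own block table. If it does, site is a randomization factor as well.

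**Working it through.** **Inputs from section IV.** Margin 18 mg/dl, SD 45 mg/dl, true difference 0, one-sided two-sample t-test, 80% power, 10% attrition, 90 per group.

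**Reproducing the plan's figure.** The normal approximation is n per group = 2(z₁₋α + z₁₋β)²·SD²/margin².
- One-sided 0.05: 2 × (1.645 + 0.842)² × 45²/18² = 2 × 6.18 × 6.25 ≈ 77.3, so 78. The noncentral t gives power 0.8001 at 78.
- One-sided 0.025: 99 by the normal formula and 100 by noncentral t. The stated 78 therefore implies one-sided 0.05.
- Attrition: 90 × 0.9 = 81 evaluable per group. SE = 45 × √(2/81) = 7.07, noncentrality 18/7.07 = 2.55, power 0.8133. The claim of more than 80% power holds.

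**Effect of adjustment.** The documents give no correlation r between randomization BG and mean daily BG, so a range is assumed. Simulation: 40,000 trials per setting, 162 patients, blocks of 4 within BG stratum, cut at the median, normal data, SD 45, one-sided 0.05. The Monte Carlo SE is about 0.2 point for power and 0.1 point for error.

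| Assumed r | Power: unadjusted | Power: stratum | Power: stratum + continuous BG | Error at a true 18 mg/dl difference: unadjusted | Error: fully adjusted |
|---|---|---|---|---|---|
| 0 | 81.3% | 81.3% | 81.0% | 0.051 | 0.050 |
| 0.2 | 81.6% | 82.2% | 82.5% | 0.046 | 0.048 |
| 0.3 | 82.0% | 83.3% | 84.2% | 0.045 | 0.050 |
| 0.5 | 83.4% | 86.9% | 90.0% | 0.037 | 0.049 |

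The full gains are 82.5 − 81.6 = 0.9, 84.2 − 82.0 = 2.2 and 90.0 − 83.4 = 6.6 points.

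**Analytic cross-checks.**
- Power: adjustment leaves a residual SD of 45√(1 − r²). At r = 0.3 this is 45 × 0.954 = 42.9. The noncentral t at SD 43 and 81 per group gives 0.8432, against 0.842 simulated.
- Error: a median split of a normal covariate carries a share 2/π of r². The unadjusted error is then about Φ(−1.645/√(1 − 2r²/π)). At r = 0.5 this is Φ(−1.645/0.917) = Φ(−1.79) ≈ 0.036. At r = 0.3 it is Φ(−1.645/0.971) = Φ(−1.69) ≈ 0.045. Both agree with the simulation.

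**Sensitivity.**
- SD 40 (illustrative, below the stated bound): 88.8 to 89.5% (r = 0.2), 89.3 to 91.0% (r = 0.3), 90.5 to 94.9% (r = 0.5). The gain is smaller.
- Cut moved half an SD either side of the mean (31/69% split): full-model power changes by at most 0.4 point.
- Separate tables at three sites (assumed 40/30/30% split), site added to the full model: no visible change if site explains none of the variance, about half a point gained if it explains 2%, and about one point if it explains 5%.
- Losses above 10%: at 72 per group (90 × 0.8, illustrative), the unadjusted noncentral-t power is 77.2%. Simulation at r = 0.3 with 72 per group gives 78.4% unadjusted and 80.8% adjusted.

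**The case against.** The strongest reply is that nothing here is wrong: the t-test is valid, errs on the safe side, and reaches its stated power. That is correct, and it is why the point is an optional improvement.

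The second reply is that r may be low. Eligibility caps randomization BG below 400 mg/dL. The starting dose for insulin-naive type 2 patients rises with randomization BG. Doses are titrated daily, and the first day is left out: "Hospital glucose values after the first day of insulin treatment will be included in the analysis". All of this weakens the link between entry BG and later mean BG. At r = 0.1, a 10,000-trial simulation gives 81.4% unadjusted and 81.3% adjusted, so no gain. This stands as a limit on size. It does not argue against adjusting, because the cost at r = 0 is only about 0.3 point.

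Third, the stratum adds nothing to power once continuous BG is in the model (r = 0.3: 83.9% with continuous BG alone, 83.8% with both). That is true, but keeping the stratum costs nothing measurable and makes the analysis match the allocation.

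Fourth, larger open questions remain. Alpha is unstated, the text speaks of both non-inferiority and an equivalence margin, and the primary outcome differs between sections. At one-sided 0.025, power at 81 per group would be 71.6%. These questions are real and separate; adjustment does not settle them. The power figures apply to mean daily BG only, and no gain has been shown for time in range.

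**Conclusion.** The concern holds as an efficiency and pre-specification gap. The plan balances allocation on a factor that its analysis never names, and the comparison against the 18 mg/dl margin has no adjusted model. The stated sample size and the validity of the t-test are unaffected.

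With 81 evaluable per group, SD 45 and one-sided 0.05 (inferred from the 78), the benefit is roughly 1 to 2 points of power at r = 0.2 to 0.3, and up to about 6.6 points at the high-end r = 0.5. Adjustment also brings the error rate back to about 0.05 from 0.045–0.046 (r = 0.2 to 0.3) or 0.037 (r = 0.5). Every one of these gains rests on an assumed correlation. What does not depend on r is that adjustment is nearly costless and removes a choice that would otherwise be left open for the main claim.

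**What to change.** Add to the analysis text of section IV:

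*Mean daily BG will be compared between arms by linear regression on arm, randomization BG stratum (≤200 / >200 mg/dL) and continuous randomization BG. Non-inferiority will be concluded if the upper one-sided 95% confidence bound for the adjusted CGM minus POC difference lies below 18 mg/dl. The unadjusted t-test will be a sensitivity analysis.*

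The 95% bound follows from the plan's own 78 per group; the sponsor should confirm that level in writing. The text should also:
- make clear that this model, and not the Wilcoxon test, serves the margin comparison;
- use the same covariates for time in range, reporting the difference with its confidence interval, since no margin is set for it;
- state whether block tables are separate by institution and, if so, include site in the models;
- name the covariates in the secondary-outcome regression sentence.

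The cost is a few sentences. Randomization BG and site are already known when the block table is used. The change does not decide which efficacy outcome is primary. Section IV says "The primary efficacy endpoint is glycemic control measured by mean daily BG concentration and time in range", while the outcomes list in section III names time in range alone, so the sponsor must resolve that separately.

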Aim 1. To determine differences in glycemic control, as measured by the percentage of time in range between 80-180 mg/dl (efficacy outcome) and frequency of hypoglycemia (safety outcome), between DexcomG6 CGM and POC BG testing in hospitalized patients with T1D and T2D treated with basal bolus insulin regimen. Adult patients with T1D and T2D requiring basal bolus insulin therapy will be randomized to POC testing (standard of care) or to Dexcom G6 CGM to guide daily insulin dose adjustment. All patients will receive POC testing before meals and bedtime as well as a Dexcom CGM device. Patients in the POC testing group will wear a blinded CGM and providers will adjust insulin dose based on POC results. Providers in the CGM group will adjust insulin dose based on daily glucose profile information.

Hypothesis: The use of CGM will result in similar glycemic control but will improve detection and reduce the frequency of clinically significant hypoglycemia (<54 mg/dl) and severe hyperglycemia (>250 mg/dl) compared to standard POC testing in insulin treated patients with T1D and T2D.

Aim 2. To examine differences in glycemic control after hospital discharge between Dexcom G6 CGM and POC BG testing in hospitalized patients with T1D and T2D. Patients enrolled in Aim 1 who will be discharged on insulin therapy (+/- oral agents) will be invited to participate in this prospective exploratory study. All patients, regardless of inpatient treatment arm, will be discharged with a blinded CGM device placed either on the abdomen or arm at physician discretion. The total duration of the study is 10 days. Downloading of the sensors will be performed prior to discharge and 10 days after hospital discharge.

Hypothesis: Glucose monitoring by CGM will improve detection of clinically significant hypoglycemia (<54 mg/dl) and severe hyperglycemia (>250 mg/dl) compared to standard POC after hospital discharge in patients with T1D and T2D.

II. BACKGROUND AND STATUS OF WORK IN THE FIELD.

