The Dexcom G6 CGM is a commercially available factory-calibrated sensor system ³², thus there is no need for POC BG testing for sensor calibration. Performance/accuracy data for 10-days have reported excellent correlation with glucose values reported by laboratory and POC testing. The benefits of factory-calibrated CGM sensors include replacing the need for finger-stick blood glucose monitoring and providing the benefits of real-time glucose values in adjusting insulin therapy during hospitalization and after discharge. The proposed prospective RCT will be the first to test the efficacy and safety of Dexcom G6 CGM in adjusting daily insulin dose in medicine and surgery patients with T1D and T2D in non-ICU settings.

DexcomG6 Glucose Telemetry System

System. The system includes 3 main devices, i) DEXCOM G6 CGM device (sensor, transmitter, ii) a smart phone, and iii) a tablet computer. As a first step glucose values obtained from the CGM sensor are sent to the CGM transmitter by Bluetooth technology and DEXCOM Share2 software application to a smart phone that serves as an intermediate-transmitting (routing) device. This study phone will be locked in a safe box located in the patient's room. With the help of commercial internet wireless network, glucose values from the smart phone will be transmitted wirelessly to a table computer (I-Pad) using the DEXCOM Follow application [<https://www.dexcom.com/apps>].

CGM alarm settings, and prevention of hypoglycemia protocol. Hypoglycemia alarms will be set to < 80 mg/dl (for prevention for low blood glucose levels). Nursing staff will be instructed to provide 15 grams of carbohydrates in response to a hypoglycemia alarm. For control group (blinded CGM) CGM alarms are turned off, however if the POC is found to be between <80 mg/dl, 15 grams of carbohydrates will be given as a preventive measurement to avoid clinically significant hypoglycemia.

[figure not shown]
Patients will receive education on the CGM technology by our research team. Similar education efforts are applied targeting nursing and medical staff, including how and when to remove or replace CGM sensors and transmitters and about the hypoglycemia prevention protocol. Treatment of hypoglycemia (POC <80 mg/dl) will be similar in both groups following a standard hospital protocol.

III. STUDY DESIGN AND METHODS

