- Patients with admission HbA1c < 7.5% will be discharged on their preadmission antidiabetic regimen.
- Patients on oral agents prior to admission with an HbA1c between 7.5% and <10% will be discharged on oral agents plus basal insulin (glargine, detemir, degludec) at 50% of the daily hospital dose.
- Patients on oral agents prior to admission with an admission A1C ≥ 10% will be discharged on their oral agents plus basal insulin at 80% of daily hospital dose.
- Patients on oral agents plus basal insulin (NPH, glargine, detemir) prior to admission with an admission A1C between 7.5% and <10% will be discharged on their oral agents plus basal insulin at 50% of daily hospital dose.
- Patients on oral agents plus basal insulin (NPH, glargine, detemir) prior to admission with an admission A1C ≥ 10% will be discharged on their oral agents plus basal insulin at 80% of daily hospital dose.
- Patients treated with basal bolus regimen prior to admission will be discharged on 80% of their preadmission TDD with basal insulin once daily and rapid-acting insulin before meals.

Follow-up Care:

- Duration of post discharge study: ~10 days (participant can return sooner or later depending on his/her schedule)
- New CGM (blinded) sensor will be placed (abdomen or arm at investigator's discretion) before discharge. If primary care team is planning to discharge over the weekend: participants will get new blinded sensor on Friday evening prior to discharge. The real time CGM will be left in the abdomen to continue to monitor during hospital stay. Participant will be asked to return on the following business working day to remove real time CGM. Blinded sensor (placed before discharge) will be removed at 10 day follow up visit after discharge.
- Patients will be asked to continue checking their blood glucose by regular POCT and will return to the outpatient clinic visit at 10 days after discharge (sooner or later depending on participant's availability and schedule).

The following information will be collected after discharge:

1. Glycemic control:
 - a. Mean daily blood glucose by CGM and POC testing
 - b. Time in range (80-180 mg/dl)
 - c. Frequency of overall clinically significant hypoglycemia (<54 mg/dl) and severe hyperglycemia (>250 mg/dl).
 - d. Nocturnal hypoglycemia < 70 mg/dl and < 54 mg/dl (between 22:00 and 06:00)
 - e. Duration or time in hypoglycemia (minutes) during the day and night
 - f. Frequency and duration of time in hyperglycemia > 240 mg/dl

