providers that a patient maybe at risk of hypoglycemia. If this occurs, the nursing staff will meet patient in the room to assess clinical status and signs/symptoms of hypoglycemia and will perform a POC glucose testing. A carbohydrate load of 15 grams will be provided to patients to avoid clinically significant hypoglycemia.

Clinically significant hypoglycemia defined as POC <80 will be treated per hospital protocol in both groups.

Nursing staff should perform a POCT BG if the patient complains of symptoms of hypoglycemia, even in the absence of CGM alarms. POCT BG should be treated accordingly.

Insertion of the CGM sensor will be performed per manufacturer instructions and following an aseptic technique. After insertion of the sensors, providers will ensure proper hemostasis is achieved. Sensors will be removed if prolonged bleeding or severe pain occurs.

Recruitment and Consent. Coordinators will screen for potential participants from the electronic medical record. Subjects will be provided with sufficient information on the practice of glucose monitoring before providing written consent. The process of obtaining informed consent will follow the standard procedures of Emory University. This protocol will be submitted for approval by the Emory IRB.

Potential Benefits to Human Subjects. Subject participating in this trial will not receive any direct benefits during the hospital stay, since treatment decision will be made based on POC BG (standard of care). In the outpatient arm, investigators will analyze glucose profiles in a more detailed manner with potential for better treatment modifications.

Inclusion of children. No patients under the age of 18 will be recruited in this study.

Confidentiality. Informed consent will follow the procedure of Emory University Institutional Review Board. Every potential participant will be informed in writing and verbally with the important and key points of the study. One of the investigators or research coordinators will obtain a witnessed informed consent prior to inclusion of a patient into the study. Data collection records with personal identifiers will be stored in locked file cabinets. Presentation of the study results at regional or scientific meetings or in publications will not identify subjects. Access to research and confidential records will be limited to clinical investigators, coordinators and the IRB at Emory University.

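### The primary safety outcome is hypoglycemia below 54 mg/dl, but the plan's own set of analysis definitions puts the same term at below 56 mg/dL

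*Combined protocol and SAP*

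**What the plan says.** Section III, Primary and Secondary Research Outcomes, names the primary safety outcome as "Clinically significant hypoglycemia <54 mg/dl (safety outcome". The Aim 1 hypothesis in the Specific Aims says that CGM will "reduce the frequency of clinically significant hypoglycemia (<54 mg/dl"), and the Aim 2 hypothesis uses the same cut-off. The post-discharge list under Follow-up Care, item c, has "Frequency of overall clinically significant hypoglycemia (<54 mg/dl) and severe hyperglycemia (>250 mg/dl").

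Section V, Potential Risk to Human Subjects, paragraph on hypoglycemia, gives three tiers in a row. The first reads "In this analysis, hypoglycemia is defined as a BG or IG < 70 mg/dL". The second reads "Clinical significant hypoglycemia is defined as BG or IG < 56 mg/dL". The third puts severe hypoglycemia below 40 mg/dL.

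Section IV, Statistical Methods, says that hypoglycemia incidence will be calculated from CGM and POC data but gives no threshold.

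Two further places bear on the point:

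- Section V, CGM alarms and hypoglycemia protocol: "Clinically significant hypoglycemia defined as POC <80 will be treated per hospital protocol in both groups". The telemetry system description in section II uses the same level without the outcome term: "Treatment of hypoglycemia (POC <80 mg/dl) will be similar in both groups following a standard hospital protocol".
- Follow-up Care, item f: "Frequency and duration of time in hyperglycemia > 240 mg/dl". Item c of that list and inpatient secondary outcome 4 use 250 mg/dl.

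**The concern.** A primary outcome needs one event definition, fixed before the data are seen. Here the outcome list and the analysis definitions give the same named event two cut-offs, and no text says which takes precedence. The section V set is also the only place that defines all the hypoglycemia tiers together and states the measurement basis (blood or interstitial glucose). A programmer who finds no cut-off in Statistical Methods could reasonably take it from there.

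If that happened, a patient whose lowest reading was 54 or 55 mg/dl would count as having the primary safety event, although the declared outcome says otherwise. Leaving two cut-offs in the plan also invites a later question about whether the choice was made after seeing results.

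The use of the outcome term for POC below 80 is a labelling problem. It applies the name of the primary safety event to a level above the plan's own limit for any hypoglycemia (below 70). Elsewhere the plan treats 80 as a treatment or preventive level, so this is not a competing endpoint.

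**Working it through.** **Step 1. Count the uses of each cut-off.**

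| Place | Cut-off (mg/dl) | Uses |
|---|---|---|
| Specific Aims, hypotheses for Aims 1 and 2 | <54 | 2 |
| Section III: primary safety outcome, secondary outcomes 1 and 2 | <54 | 3 |
| Follow-up Care, items c and d | <54 | 2 |
| Section V, hypoglycemia risk paragraph | <56 | 1 |

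The 54 mg/dl value therefore appears 2 + 3 + 2 = 7 times and 56 once. Dividing by 18, the two are 54/18 = 3.00 and 56/18 = 3.11 mmol/l. If values are recorded in whole mg/dl, the readings in dispute are exactly 54 and 55.

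**Step 2. Does the sample size depend on the cut-off?** Section IV bases it on mean daily glucose: margin 18 mg/dl, SD 45 mg/dl, true difference 0, one-sided two-sample t-test, 80% power, 78 per group. The document states no alpha; 0.05 one-sided is assumed because it reproduces the figure. The noncentrality at n = 78 is 18 / (45 × √(2/78)) = 2.498, and the power is 0.8001. The stated 78 is reproduced. No hypoglycemia threshold enters the calculation, so the choice between 54 and 56 leaves it unchanged.

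**Step 3. How much could the 2 mg/dl matter?** The documents give no event rate below 54 or 56 and no distribution of individual readings, so the effect on event counts cannot be calculated. As an illustration only, assume a mean m of 150 to 190 mg/dl (steps of 10) and a coefficient of variation of 0.30, 0.36 or 0.42. The quantity is the proportion of time below each cut-off x:

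- Normal shape: P(x) = Φ((x − m) / (CV × m)).
- Log-normal shape: P(x) = Φ((ln x − μ) / s), with s² = ln(1 + CV²) and μ = ln m − s²/2.
- Extra minutes a day = 1440 × (P(56) − P(54)).

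Worked case, m = 170 and CV = 0.36:

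- Normal: (54 − 170)/61.2 = −1.895 and (56 − 170)/61.2 = −1.863. This gives 2.902% and 3.125%, a ratio of 1.077 and 3.2 extra minutes a day.
- Log-normal: s = 0.349, μ = 5.075. This gives 0.093% and 0.132%, a ratio of 1.416 and 0.56 extra minutes a day.

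Over the whole grid:

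| Shape | Ratio, <56 to <54 | Extra minutes a day |
|---|---|---|
| Normal | 1.054 to 1.116 | 1.22 to 5.85 |
| Log-normal | 1.268 to 1.703 | 0.02 to 3.79 |

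The largest ratio (1.703) comes from the smallest tail, 0.0017% against 0.0030%, and so represents almost no time. The relative effect depends strongly on the assumed shape; the absolute effect is small under both.

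**The case against.** The strongest reply is that 56 is a typing slip. The value 54 appears seven times, including in the section whose purpose is to list the outcomes. The single 56 is in a human-subjects risk paragraph, next to a literature range for hypoglycemia risk, and not in Statistical Methods. The words that tie the definitions to the analysis are in the preceding sentence, which concerns the 70 mg/dL tier. Any cut-off would apply to both arms, so nothing in the text points to bias between them.

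Most of this stands. The intended cut-off can be inferred, and no between-arm bias is claimed. But an inferable intent makes the correction easy without making it unnecessary. The three tiers read as one set, and Statistical Methods offers nothing to override them.

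The illustration is also open to criticism. Its means and CVs are not from the documents, and time below a threshold is not an event count. The normal shape implies about 12 to 92 minutes a day below 54, which sits poorly with section V's expectation that about 10% of inpatients will have an episode (though that may refer to episodes found by POC testing). Those limits are accepted: the figures show only that the absolute effect is probably small, and the point does not rest on them.

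On hyperglycemia, item c carries the word severe and item f does not, so 250 and 240 could be separate descriptors. However, item f otherwise matches inpatient secondary outcome 4 in wording and differs only in the number. It affects an exploratory aim, with no inpatient-versus-discharge comparison specified, and is minor.

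**Conclusion.** The concern holds. The plan carries two cut-offs for its primary safety outcome, and the one in its set of analysis definitions does not match the declared outcome. The discrepancy is 2 mg/dl and concerns readings of 54 and 55. Its effect on the number of events or patients affected cannot be calculated from the documents. The illustrative effect on time below threshold is at most about 6 minutes a day under the assumed means, CVs and shapes. Sample size and power are unaffected. It should be corrected because it touches a primary outcome, although the numerical consequence is likely to be small and the intent is clear. The use of the outcome term for POC below 80 is a labelling conflict, and the 240 versus 250 mismatch is minor.

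**What to change.** In section V, Potential Risk to Human Subjects, change the definition of clinically significant hypoglycemia to below 54 mg/dl so that it agrees with the declared primary safety outcome.

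Two wording reconciliations should go with it:

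- Reconcile the section V alarm protocol with the descriptions of the POC below 80 level in sections II and III, so that the outcome term is not attached to that level. No change to the treatment trigger is proposed.
- Reconcile Follow-up Care item f (240 mg/dl) with item c and inpatient secondary outcome 4 (250 mg/dl), or state that the difference is intended.

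The cost is one corrected line and two wording changes, with no effect on sample size, data collection or conduct.
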